Protocol Title: Ultrasound Microbubble Destruction for Improving Radioembolization Therapy of Hepatocellular Carcinoma

Trial Objectives: The primary objective of this trial is to:

· Characterize the ability of localized ultrasound contrast agent destruction to improve hepatocellular carcinoma (HCC) response to Y90 radioembolization.

The secondary aim of this trial is to:

· determine if contrast-enhanced ultrasound estimated tumor perfusion can reliably predict HCC response to radioembolization 1-14 days post treatment.

Trial Design: This is an open-label, randomized trial that will be conducted at one clinical site to determine if ultrasound-triggered microbubble destruction (UTMD) can be used to improve radioembolization of HCC. The subject population will be patients scheduled for radioembolization of a previously untreated HCC mass at Thomas Jefferson University. Patients will be randomly assigned to either the experimental (UTMD + radioembolization) or control group (radioembolization alone) by the research coordinator using a random assignment generator. For patients assigned to the experimental group, the study will consist of up to three contrast-enhanced ultrasound (CEUS) exams 1-6 hours post radioembolization, and approximately 7 and 14 days post treatment. Treatment response will be evaluated using modified response evaluation criteria in solid tumors (mRECIST) at 1 and 3-4 months post treatment based on the patient's clinically scheduled contrast-enhanced MRI or CT. For patients assigned to the control group, only outcomes data will be collected (without intervention).

Ultrasound imaging will be performed using a state of the art commercial ultrasound scanner with a curvilinear transducer. As part of each CEUS exam, patients will first undergo baseline grayscale B-mode and power Doppler imaging (PDI) of the treated mass. Patients will then receive an infusion of the ultrasound contrast agent (UCA) Optison (GE Healthcare, Princeton, NJ), while being imaged with two-dimensional (2D) dual mode B-mode / coded harmonic imaging. Once the presence of contrast has been confirmed in the tumor, a series of flash-replenishment sequences will be generated to destroy UCA within a region of interest encompassing the tumor. This sequence will be repeated at imaging planes throughout the tumor for the duration of the infusion.

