Treatment response of HCC to radioembolization is monitored using contrast-enhanced MRI or CT at 1 month and 3-6 months post treatment response. An earlier predictor of treatment response would be clinically beneficial as HCC patients are still eligible for chemoembolization or ablation post radioembolization. Changes in tumor perfusion have been identified as early indicators of HCC treatment response [Zocco et al 2013; Murakami et al. 2011]. Tumoral inflammation in the microenvironment may also be an early indicator of effective treatment [Serres et al. 2014]. Accurate quantification of tumoral perfusion is difficult using MRI or CT techniques, however, due to their relatively low temporal resolution.

CEUS, which has relatively high temporal resolution, has been able to identify inflammation-related changes in perfusion in other diseases, [Saevik et al. 2014] and thus may be useful in identifying inflammation following radioembolization. Ultrasound contrast agents are well tolerated and administered intravenously, making them an ideal noninvasive screening tool. Commercially available contrast imaging packages are now available on most ultrasound scanners. When insonated at sufficient acoustic pressures (MIs > 0.5), UCA undergo inertial cavitation and localized collapse [Goldberg et al. 2001]. This behavior

forms the basis of flash-replenishment imaging, in which reperfusion within an imaging plane can be repeatedly imaged using cycles of destructive pulses followed by lower MI imaging to monitor reperfusion. These flash-replenishment sequences can performed using commercially available packages that generate a higher intensity (but still well within FDA MI limits) pulse within a selected region of interest. Our group and others have also shown that blood perfusion can be quantified by measuring the rate of contrast perfusion after either a bolus injection or during flash-replenishment imaging using nonlinear CEUS [Sridharan et al. 2013; Wei et al. 1999; Gauthier 2011]. These techniques have been utilized clinically in the liver using commercially available flash-replenishment packages to quantify liver and liver tumor perfusion [Wakui et al. 2011; Shiraishi et al. 2008; Lefort, et al. 2012].

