1.2 Rationale

The fundamental theory behind this study is that localized UCA cavitation within the tumor vasculature will sensitize this tissue to Y-90 radiation and improve patient outcomes. Additionally, we hypothesize that quantification of UCA reperfusion following flash destructive ultrasound pulses will reflect inflammation changes, and provide an earlier predicator of radioembolization treatment response. If UCA

cavitation leads to effective sensitization of HCC to radioembolization, such an approach would improve treatment efficacy and prolong survival. If CEUS-based perfusion measurements were found to accurately predict treatment response, non-responding patients could be identified earlier and scheduled for alternative therapies such as chemoembolization or ablation (which in turn would also prolong survival).

We propose a pilot clinical trial to determine the potential of using CEUS flash-replenishment imaging for improving radioembolization therapy and predicting tumor response. The purpose of this study is to compare tumoral response in 26 patients treated with this approach to 26 patients treated via standard of care (radioembolization alone) and also to determine if quantitative CEUS data acquired from the experimental arm can predict future RECIST outcomes.

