3. TRIAL DESIGN

This is an open-label, randomized trial that will be conducted at one clinical site to determine if ultrasound-triggered microbubble destruction (UTMD) can be used to improve radioembolization of HCC. The subject population will be patients scheduled for radioembolization of a previously untreated HCC mass at Thomas Jefferson University. All patients will undergo single-photon emission computed tomography (SPECT) imaging as part of their standard of care to confirm effective localization of the Y90 beads. For research purposes, imaging of the chest will be performed when possible to assess extrahepatic distribution of Y90 using a planar imaging acquisition. Patients will be randomly assigned to either the experimental (UTMD + radioembolization) or control group (radioembolization alone) by the research coordinator using a random assignment generator. For patients assigned to the experimental group, the study will consist of up to three contrast-enhanced ultrasound (CEUS) exams: 1-6 hours post radioembolization, and approximately 7 and 14 days post treatment. Treatment response will be evaluated using modified response evaluation criteria in solid tumors (mRECIST) at 1 and 4 months post treatment based on the patient's clinically scheduled

contrast-enhanced MRI or CT. For patients assigned to the control group, only outcomes data will be collected (without intervention).

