4. TRIAL POPULATION

Trial Population: This trial will consist of up to 104 adults (18 years of age or older) undergoing radioembolization of a previously untreated HCC mass less than 6 cm in diameter.

Subjects eligible for trial enrollment will be identified by the co-investigators from their patient population of subjects being seen for radioembolization of HCC. These patients will be accrued from the Hepatology department, as well as from the HCC Multidisciplinary Tumor Board of the Kimmel Cancer Center at Thomas Jefferson University. A research coordinator will explain the study to the patient. The patient will be given time to consider the risks and benefits of the study and ask questions about participation. The coordinator will review the consent form with the patient and then the patient will be given the form to review. The patient, coordinator, and a study investigator will all sign the consent form. The patient will be given a copy of the signed consent form for their records.

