5.4 Blinding and Unblinding Methods

No blinding will be performed as this is a pilot study and all data analysis will be performed immediately following ultrasound intervention.

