CEUS studies will only be conducted with patients assigned to the experimental group (UTMD + radioembolization). Five milliliters of activated Optison will be suspended in 50 ml of saline and infused through an angiocatheter placed in a peripheral arm vein at a rate of 120 ml/hour. This total Optison administration falls within the product insert dosage guidelines (up to 5 ml within a 10 minute period and up to 8.7 ml in any one study). After confirmation of contrast-enhancement within the mass, a series of ultrasound-triggered microbubble destruction (UTMD)-replenishment sequences will be generated to cavitate UCA within the imaging plane. The patient will be asked to temporarily halt respiration while a 4 second UTMD pulse is initiated (approximate transmit parameters of MI = 1.13 at 1.5 MHz, transmitting 2.3 µs pulses at a pulse repetition frequency of 100 Hz), followed by nonlinear imaging of contrast replenishment at lower intensity using Cadence Pulse Sequencing (MI = 0.06) for 10 seconds. Following patient respiration, this sequence will be repeated at multiple imaging planes throughout the tumor and then repeated throughout the entire tumor volume for the duration of the infusion (UTMD expected in 10-20 planes, repeated 3-4 times). In the few patients with multiple Y-90 treated tumors, the largest tumor will be selected for UTMD therapy and outcomes compared to the non-UTMD treated tumors outside the acoustic field. This sequence will be repeated at imaging planes throughout the tumor for the duration of the infusion. Following completion of the infusion, patients receiving ultrasound contrast agent will be monitored for adverse events for 30 minutes to ensure stable response.

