6.5 Efficacy Assessments

The primary measure of tumor response will be evaluated using mRECIST criteria as determined by Drs. [name] and [name] in consensus using the patients clinically scheduled 3-4 month contrast enhanced MRI or CT. As a secondary measure of tumor response, changes in alpha fetal protein (AFP; collected as blood samples at 1 month as standard of care) will be recorded. Finally, each patient's progression free survival and overall survival will be monitored, although this is a tertiary outcome for this study and many patients are expected to surpass the timeline of this pilot study. Safety outcomes will be determined using changes in vital signs, observed and self-reported adverse events, and changes in liver function tests (LFTs) at 1 and month post-embolization (preformed as part of clinical standard of care). Liver function tests

(LFTs) include blood tests for alanine aminotransferase, alkaline phosphatase, asparate aminotransferase, bilirubin, albumin, total protein, and prothrombin time. SPECT imaging will be evaluated for all available cases by two blinded radiologists to evaluate if the initial UTMD session skews Therasphere distribution in the liver.

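### Day 7 and day 14 perfusion data exist only in the UTMD arm, and nothing keeps them from treating clinicians or mRECIST readers before the 3-4 month read

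*Combined protocol and SAP*

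**What the plan says.** Section 6.3 confines the imaging to one arm: "CEUS studies will only be conducted with patients assigned to the experimental group (UTMD + radioembolization". Section 3 sets the schedule as "up to three contrast-enhanced ultrasound (CEUS) exams: 1-6 hours post radioembolization, and approximately 7 and 14 days post treatment". For controls, section 3 provides for collection of outcomes data and nothing else.

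On masking, section 5.4 reads in full: "No blinding will be performed as this is a pilot study and all data analysis will be performed immediately following ultrasound intervention". The only reads called blinded are the SPECT reads (section 6.5).

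The primary endpoint is mRECIST, judged by two readers "in consensus using the patients clinically scheduled 3-4 month contrast enhanced MRI or CT" (section 6.5). Time to next treatment appears once, in section 7.2.1, among further between-arm comparisons. Aim 2 correlates normalised perfusion with later mRECIST within the UTMD arm (section 7.2).

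On further therapy, section 1.1 notes that "HCC patients are still eligible for chemoembolization or ablation post radioembolization". Section 1.2 says that if CEUS perfusion is found to predict response accurately, "non-responding patients could be identified earlier and scheduled for alternative therapies such as chemoembolization or ablation". Section 4 has eligible patients "identified by the co-investigators from their patient population of subjects being seen for radioembolization of HCC".

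**The concern.** Randomisation balances patients at baseline. It does not balance information that is generated afterwards in one arm. Here the UTMD arm receives the intervention and also yields a perfusion change at about days 7 and 14 that has no counterpart in controls. The plan describes no separation between the imaging team, the treating clinicians and the mRECIST readers.

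Three analyses are exposed:

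- **3-4 month mRECIST.** If a perfusion result prompts additional therapy before the scan, the comparison is of UTMD plus extra monitoring against standard follow-up, and no longer isolates radiosensitisation. A reader who has seen the perfusion result may also be influenced by it.
- **Time to next treatment.** Any CEUS-prompted therapy shortens this time in the UTMD arm only.
- **Aim 2.** Therapy prompted by perfusion, or an mRECIST read made with knowledge of it, alters the outcome that perfusion is supposed to predict.

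**Working it through.** **1. The plan's own figure.** Section 7.2.1 gives 52 per group for 85% power, effect 0.6 and 5% type I error. I read 0.6 as a standardised difference and the test as two-sided (sidedness is not stated for Aim 1). Then n = 2 × ((1.960 + 1.036)/0.6)² = 49.9, or 50 per group. Dividing by the Mann-Whitney efficiency 3/π gives 52.2, or 53 per group. Power at 52 is 84.8% with that correction and 86.4% without it. The figure reproduces, and nothing below changes the sample size.

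**2. The one-sided window.** Both arms have a 1-month MRI or CT (section 7.2). Perfusion is normalised to day 1 (section 6.5), so the 1-6 hour exam is the baseline and the first change from it is available at about day 7. Taking 1 month as 30 days, the extra lead in the UTMD arm is 30 − 14 = 16 to 30 − 7 = 23 days, roughly 2-3 weeks.

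**3. Effect on the false-positive rate.** The documents give neither the mRECIST distribution nor a rate of further therapy, so both are assumptions. Take no true UTMD effect, 52 per arm, and complete response, partial response, stable disease and progressive disease (CR/PR/SD/PD) at 40/30/20/10% in both arms. Let a net fraction δ of all UTMD patients move from SD/PD to CR, in proportion to SD and PD, and be scored as they look.

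- Mid-rank scores (proportion in better categories plus half the category): CR 0.20, PR 0.55, SD 0.80, PD 0.95.
- Average score for SD/PD: (0.20 × 0.80 + 0.10 × 0.95)/0.30 = 0.85. Each patient who moves gains 0.85 − 0.20 = 0.65.
- Tie-corrected variance: (1 − (0.4³ + 0.3³ + 0.2³ + 0.1³))/12 = (1 − 0.100)/12 = 0.075.
- Standard error of the difference: √(0.075 × 2/52) = 0.0537.
- Shift of the test statistic: m = 0.65δ/0.0537 = 12.1δ.
- Rejection rate: Φ(m − 1.96) + Φ(−m − 1.96).

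| Net shift δ | Patients of 52 | m | Formula | Simulation |
|---|---|---|---|---|
| 1% | 0.5 | 0.12 | 5.2% | 5.1% |
| 2% | 1.0 | 0.24 | 5.7% | 5.5% |
| 3% | 1.6 | 0.36 | 6.5% | 6.3% |
| 5% | 2.6 | 0.61 | 9.3% | 9.2% |
| 10% | 5.2 | 1.21 | 22.7% | 22.8% |

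The simulations used the tie-corrected Mann-Whitney test with 4,000 trials (1-3%) or 6,000 trials (5-10%) per setting. A 50/25/15/10% mix gives about 9% and 23% at δ = 5% and 10%. A 15% shift would give about 46%, but it needs half of all SD/PD patients (15 of 30 percentage points) to become CR because of CEUS, so I treat it as outside the useful range.

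**4. A milder mechanism.** Suppose a fraction f of all non-CR UTMD patients receive CEUS-prompted therapy, and either half of them become CR or all of them are left out of the analysis. With mixes of 40/30/20/10% and 50/30/15/5%, the rejection rate is 5-6% at f = 10%, 7-8% at 20%, 11-14% at 30% and 24-32% at 50%. At f of 20% or more, nearly all rejections favour UTMD.

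**5. Direction.** The results in steps 3 and 4 depend on scoring lesions as they look or excluding re-treated patients. If re-treated patients were scored as failures, the bias on mRECIST would run against UTMD. The plan gives no rule for therapy received before the 3-4 month scan.

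**The case against.** The best defence is that the plan describes no actionable read. A reader might infer from section 1.2 that perfusion is measured in order to send non-responders to other therapy during the trial. The text does not support that: the sentence is conditional on CEUS proving predictive and describes a later benefit. No section says CEUS results direct care.

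A reader might also take the 1-6 hour exam as an early response signal, but it is the normalisation baseline. The perfusion output needs curve fitting, multi-slice volumes and region selection, and no threshold for non-response is given. Even the expected direction is unclear, since section 1.1 suggests that inflammation may accompany effective treatment.

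The claim of immediate analysis cannot be literal either. The primary analysis needs 3-4 month scans, and section 3.1 schedules 3 months of analysis after recruitment.

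Finally, the 1-month scan can prompt therapy in both arms, which narrows the net difference, and time to next treatment is not among the primary, secondary or tertiary measures in section 6.5.

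All of this stands, and it lowers the likely size. It does not close the gap. Section 5.4 disclaims blinding and gives early analysis as a reason, the outputs may exist months before the endpoint is read, and no section restricts who sees them. The blinded SPECT reads show that selective masking is workable in this open-label trial.

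**Conclusion.** The point holds as an unguarded route to bias. The documents do not show that bias will occur. Information available in one arm only can reach those who choose further therapy and those who read mRECIST, and it can affect the primary comparison, time to next treatment and Aim 2.

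The size is unknown. Under the assumed response mix, with no true effect and 52 per arm, the error rate stays close to nominal (about 5-6%) for a net 1-3% shift from SD/PD to CR, and rises to about 9% at 5% and about 23% at 10%. The higher figures should not be read as expected values, because the documents give no rate of further therapy.

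Nor do the documents support saying that the bias must favour UTMD, or that scoring rules are irrelevant: the handling of re-treated patients decides the direction on mRECIST. Because a short wording change removes most of the risk, it should be made.

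**What to change.** In sections 5.4 and 6.3, state that quantitative perfusion outputs (α, β, their product and the parametric volumes) are held by the imaging research team, or computed only afterwards. They are not released to treating clinicians, the tumour board or the mRECIST readers until that patient's 3-4 month mRECIST is recorded. Safety and incidental findings are exempt. Section 6.5 assigns two doctors to region selection and two to mRECIST, with names removed from the public copy. If they are the same people, region selection should follow the recorded mRECIST read.

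Log any unmasking with date and reason. Record further therapy before the 3-4 month scan in both arms, report it by arm, and pre-specify how it is handled in the primary analysis, with a sensitivity analysis. Reconcile the immediate-analysis wording in section 5.4 with the end-of-trial analysis period in section 3.1.

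The cost is protocol wording and a log, with no added visits or patients. The downside is that perfusion results, whose predictive value is still the Aim 2 question, are unavailable to clinicians for 3-4 months. The live contrast image will still be seen during each session, so this limits the exposure without eliminating it.

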5.5 Storage

Optison vials will be stored in a secure refrigerator, with only the study investigators and research personnel having access. The study research coordinator will be responsible for drug suspension and inventory control.

6. TRIAL PROCEDURES

6.1 Patient Enrollment

Subjects eligible for trial enrollment will be identified by Drs. [name], [name], [name], and [name] from their patient population (approximately 52 patients annually being treated by yttrium-90 for hepatocellular carcinoma). These patients will be accrued from the Hepatology department, as well as from the HCC Multidisciplinary Tumor Board of the Kimmel Cancer Center at Thomas Jefferson University. A research coordinator will explain the study to the patient. The patient will be given time to consider the risks and benefits of the study and ask questions about participation. The coordinator will review the consent form with the patient and then the patient will be given the form to review. The patient, coordinator, and a study investigator will all sign the consent form. The patient will be given a copy of the signed consent form for their records. A research coordinator will explain the study to the patient. The patient will be given time to consider the risks and benefits of the study and ask questions about participation before providing informed consent. If the subject is a woman of childbearing potential, she will have a urine pregnancy test (the results of which will be made available to her prior to study initiation) prior to each ultrasound exam. Patients will be randomly assigned to either the experimental (UTMD + radioembolization) or control group (radioembolization alone) by the research coordinator using a random assignment generator. For patients in the experimental group, a brief abdominal ultrasound (without contrast) will also be performed prior to radioembolization to ensure the target lesion is visible on ultrasound.

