1. INTRODUCTION

Hepatocellular carcinoma is the third leading cause of cancer mortality worldwide and becoming increasingly common [Alterkruse et al. 2009]. Survival one year after diagnosis is less than 50%, and is worse in patients with advanced disease [Alterkruse et al. 2009]. Because systemic therapies have been proven largely ineffective, embolization represents the current clinical standard for treatment of non-resectable hepatocellular carcinomas [Llovet and Bruix 2003]. Embolization of HCC can be performed via

transarterial chemoembolization or radioembolization. Radioembolization for HCC is performed using TheraSpheres (BTG International). TheraSpheres consist of 20-30 µm glass beads containing yttrium-90 isotopes and the product has been authorized by the FDA with a Humanitarian Device Exemption for the treatment of unresectable hepatocellular carcinoma and our institutional review board has approved these agents for the treatment of HCC. These spheres are locally delivered via a catheter temporarily placed in the hepatic artery that supplies blood flow to the tumor thereby providing a localized and sustained release of radiation. Dosages range from 110-150 Gy. Yttrium-90 undergoes pure beta emission as it decays to stable zirconium-90 with a half-life of 64 hours and average energy emission of 0.94 MeV. The local beta emissions from this technique have been shown to provide therapeutic effect within the tumor [Herba et al. 1988; Houle et al. 1989]. Treatment response is then monitored using contrast-enhanced MRI or CT at 1 month and 3-4 months post treatment response.

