3.1 Trial Duration

Individual participation for patients within the experimental arm will be limited to 3 ultrasound exams. If patients are unable to make one of the 7, or 14 day visits they will still be eligible to participate. The first CEUS exam will take place 1-6 hours post radioembolization during the patient's clinically scheduled observation period. Exams at approximately 7 and 14 days post treatment will take place during separate visits to Thomas Jefferson University. The entire ultrasound imaging protocol will require approximately 90 mins including a 30 min observation period. For patients assigned to the control arm, no additional participation will be required. Patients who receive ultrasound contrast agent will be monitored for at least 30 minutes before being discharged. The research coordinator will obtain laboratory values, imaging data, and outcomes for comparison to the experimental group (all obtained as part of the patient's clinical standard of care). Subject recruitment is expected to last 83 months (March 2017 – December 2023). Analysis and publication of results are expected to take an additional 3 months (January 2024– March 2024). Volunteer Registry Database forms will be submitted to the National Institute of Health's Office of Regulatory Compliance and Quality at the completion of the research study.

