4.1 Inclusion Criteria

All subjects accepted for this trial must:

- Be scheduled for sub-lobar radioembolization therapy of a previously untreated HCC mass < 6 cm visible on grayscale ultrasound.
- Be at least 18 years of age.
- Be medically stable.
- If a female of child-bearing age, have a negative pregnancy test prior to each ultrasound exam.
- Have signed Informed Consent to participate in the study.

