6.2 Screening Assessments

Screening assessments will be performed prior to CEUS imaging. Trial participants will have the presence of inclusion criteria and absence of exclusion criteria verified by providing a medical history. A full demographic profile, known drug allergies or intolerances, and a review of the subject's medical/surgical history will be recorded. If the subject is a woman of childbearing age, she will have a urine pregnancy test (the results of which will be made available to the subject prior to study initiation) prior to each ultrasound exam. A brief abdominal ultrasound (without contrast) will also be performed prior to radioembolization to ensure the target lesion is visible on ultrasound.

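### The arm can be known before Y-90 is delivered, and patients who never receive Y-90 can be randomised, although the randomised treatment starts only 1-6 hours later

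*Combined protocol and SAP*

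**What the plan says.** - **Who qualifies.** Section 4.1 requires that a subject "Be scheduled for sub-lobar radioembolization therapy of a previously untreated HCC mass < 6 cm visible on grayscale ultrasound". Section 3 agrees: "The subject population will be patients scheduled for radioembolization of a previously untreated HCC mass". Receipt of Y-90 is not a condition for randomisation anywhere.
- **When the arm is assigned.** Section 5.3 says that the research coordinator uses a random generator. It gives no time point and does not say who may learn the result. Section 6.1 shows that assignment comes before Y-90: "For patients in the experimental group, a brief abdominal ultrasound (without contrast) will also be performed prior to radioembolization". The Trial Procedures part of the synopsis repeats this.
- **The same scan as screening.** Section 6.2 lists it without restricting it to one arm: "A brief abdominal ultrasound (without contrast) will also be performed prior to radioembolization to ensure the target lesion is visible on ultrasound".
- **Blinding.** Section 5.4: "No blinding will be performed as this is a pilot study". The only blinded role named is that of the two SPECT readers (synopsis and section 6.5).
- **When the randomised treatment begins.** Section 3.1: "The first CEUS exam will take place 1-6 hours post radioembolization during the patient's clinically scheduled observation period". Controls receive no study intervention.
- **Completion and numbers.** Under section 6.7 a control counts as complete on consent to data sharing alone. Section 7.2.1 needs 52 patients per group, and the synopsis caps enrolment at the same 52 per group. The plan does not say how a randomised patient without Y-90 is analysed.

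**The concern.** The trial asks whether UTMD adds to the effect of Y-90. That comparison is clean only if Y-90 is delivered independently of the arm. Randomisation balances what is fixed before assignment; it cannot balance choices made afterwards by people who may know the result. Under the current order, Y-90 delivery falls after assignment, and nothing keeps the arm from the team performing it. Section 6.1 also has investigators recruit from their own Y-90 patients, so treating and trial staff may overlap.

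The same order lets a patient be randomised whose scheduled Y-90 is then cancelled. The question does not apply to that patient, who nevertheless takes one of 104 places and either has no meaningful 3-4 month mRECIST score or dilutes the comparison.

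Neither exposure is needed, because the arm determines treatment only from the first CEUS exam onward.

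**Working it through.** **Does any step need the arm before Y-90?** The only arm-specific step placed before Y-90 is the non-contrast scan in section 6.1. It checks visibility on grayscale ultrasound, which section 4.1 requires of all subjects, and section 6.2 lists it as screening with no arm restriction. It is therefore an eligibility check that belongs before randomisation in everyone, and gives no reason to assign early. If it were done only after assignment and only in the experimental arm, it could also remove patients with non-visible lesions from that arm alone.

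**Reproducing the plan's figure.** Inputs from section 7.2.1: effect 0.6 (read as a standardised difference), power 85%, type I error 5% (sidedness is not stated for Aim 1; two-sided assumed), Mann-Whitney test.

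- Two-sample normal formula: n = 2(1.960 + 1.036)² / 0.6² = 49.9, so 50 per group.
- Divide by the Mann-Whitney relative efficiency for normal data, 3/π = 0.955: 50 / 0.955 = 52.4 per group.
- Power at 52: effective n = 52 × 0.955 = 49.7; 0.6 × √(49.7/2) = 2.99; Φ(2.99 − 1.96) = 84.8%. A simulation of 6,000 trials with normal data gave 84.0%.

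The stated 52 and 85% are reproduced. mRECIST is a short ordinal scale with ties, so the figures below are approximations on the same footing as the plan's own.

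**Illustration 1: delivery differs by arm, UTMD has no effect.** Assumed shift b, in SD units. With k = b × √(49.7/2) = 4.98b, the rejection probability is 1 − Φ(1.96 − k) + Φ(−1.96 − k).

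| Assumed shift | k | Rejection at nominal 5% |
|---|---|---|
| 0.1 SD | 0.50 | 7.9% |
| 0.2 SD | 1.00 | 16.9% |

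**Illustration 2: a share f never receives Y-90, equal in both arms.** Excluded: power at n = 52(1 − f). All analysed: power at n = 52 with the effect diluted to 0.6(1 − f).

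| Assumed f | Patients per arm | Power, excluded | Power, all analysed | Randomised per arm to keep 52 treated |
|---|---|---|---|---|
| 0 | 0 | 84.8% | 84.8% | 52 |
| 5% | 2.6 | 83.0% | 81.1% | 52/0.95, so 55 |
| 10% | 5.2 | 81.0% | 76.8% | 52/0.90, so 58 |

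The documents give no value for b or f; both ranges are assumptions.

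**The case against.** - **The harm is not documented.** A reader might infer that operators do deliver Y-90 knowing the arm, or that untreated patients are being randomised. The documents support neither. The coordinator makes the assignment, no section says that the operator is told, and no non-delivery rate is given. Section 4 even describes the population as undergoing, not merely scheduled for, radioembolization. What stands is that both can happen and that no safeguard prevents either.
- **The dose range is background.** The Introduction says "Dosages range from 110-150 Gy", and it is tempting to read the width, 150/110 = 1.36 or 36%, as the scope for bias. The sentence describes the product generally. It is not a trial dosing rule, and nothing says that operators choose within the range at delivery. It does not measure any bias and is not used above.
- **Partial checks exist.** SPECT confirms Y-90 localisation in all patients, blinded readers assess the available cases, and section 7.2.1 plans to examine confounders by regression. It would therefore be too strong to say that a difference could not be attributed to UTMD. These checks can detect some imbalance but do not prevent it. Under the current order delivery is also a post-randomisation variable, and adjusting for it is not ordinary baseline adjustment.
- **Section 6.2 weakens the evidence on timing.** If 6.2 governs and the scan is done in everyone, the scan no longer shows that the arm is known before Y-90. That is fair, but section 5.3 would then still leave the time point open, and sections 6.1 and 6.2 would still conflict.
- **Later release has a practical cost.** Section 1.1 gives 2-6 hours of observation before discharge, and a CEUS exam takes about 90 minutes under physician supervision. With equal groups, about half of the provisionally held slots would go unused. This stands as a cost, and the fix offers a fallback.

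**Conclusion.** The concern holds as a gap in safeguards. The arm is assigned before Y-90 (section 6.1 and the synopsis) with no masking, no concealment and no requirement that Y-90 has been given. The Y-90 team can therefore know the arm and untreated patients can be randomised, for no procedural gain.

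The size is illustrative only. An assumed 0.1-0.2 SD shift raises the false-positive rate from 5% to about 8-17%. An assumed 5-10% never treated lowers power from about 85% to 83-81% (excluded) or 81-77% (all analysed). These figures rest on reading 0.6 as a standardised difference, a two-sided test and the normal approximation. At 5-10% the power loss is modest, but the cap contains no allowance to absorb it. The sample size itself is not in question here. This is a cheap improvement, not a flaw that invalidates the trial.

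**What to change.** 1. Reconcile the synopsis and section 6.1 with section 6.2, so that the non-contrast visibility scan is done in every consented patient before randomisation.
2. In sections 4.1, 5.3 and 6.1, state when randomisation takes place: after consent, completed screening and documented Y-90 delivery, and before the 1-6 hour CEUS slot. Keep scheduled Y-90 as the condition for consent, and make receipt of Y-90 the condition for assignment.
3. If CEUS must be booked earlier, the coordinator may hold the assignment, concealed from those planning and delivering Y-90 until delivery is recorded. This protects delivery but does not keep untreated patients out; for that, the assignment must still be generated only after delivery. Under this fallback the plan should say how randomised patients without Y-90 are analysed.

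Cost: wording in these sections, a CEUS slot held provisionally until release, and a brief non-contrast scan in up to 52 controls if section 6.2 is not already followed for them. The required 52 per group does not change.
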